Multiple chronic conditions (MCCs) are not simply aggregates of several individual conditions. They represent overlapping conditions that often have common root causes, and when grouped together can severely impact treatment options and quality of life for the patient. Primary care providers (PCPs) face many challenges in treating patients with MCCs. They need to help patients be motivated and informed enough to effectively manage their own conditions, but must balance that with the time demands of their practice.¹⁻⁵

MCCs are common and expensive among patients aged ≥ 65 and are associated with lower quality of life, poorer response to treatment, worse medical and psychiatric outcomes, higher mortality, and higher costs of care.⁷ Treatment of MCCs focuses on medical care, but patient self-management and loneliness matter too. Numerous studies indicate that chronic conditions contribute to loneliness and loneliness in turn contributes to reduced functionality and chronic illness.¹¹⁻¹³

The primary purpose of this study is to conduct a randomized clinical trial (RCT) to examine the effects of C-CHESS--a web-based intervention--on health outcomes and healthcare use among older adults with 3 or all of the following 5 common, high-risk chronic conditions: hypertension, hyperlipidemia, diabetes, osteoarthritis and BMI of 30+. Patients in the experimental group will receive treatment as usual (TAU) plus C-CHESS. Patients in the comparison group will receive TAU+internet and links to helpful websites (e.g., NIH SeniorHealth). We assume that about half of participants will have their own computers and Internet access; we will give touchscreen laptops and provide Internet access to those who do not. The RCT will be conducted in primary care clinics that are part of the University of Wisconsin Department of Family Medicine's primary care network and the Medical University of South Carolina's Primary Care Clinics. The study will involve 330 patients age ≥ 65 who will be tracked for a total of 18 months--12 with access to the interventions and 6 months for follow up, with data collected every 6 months.

The C-CHESS Intervention

For the patient, C-CHESS (or ElderTree, as it will be known to participants) provides tools, motivation, and social support to help them manage their specific set of chronic conditions and communicate with peers and their PCP.

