1.0 STUDY OBJECTIVES

This project will test the use of an eHealth intervention called C-CHESS, to modify health behaviors and improve health outcomes in older adults with comorbid chronic diseases and health conditions.

Aim 1 Refine C-CHESS, using feedback from patients and primary care clinicians.

Aim 2 Conduct a randomized clinical trial to test 4 hypotheses:

1. *Primary outcomes:* Patients assigned to TAU+C-CHESS will have better quality of life and less primary care use (fewer visits) than those assigned to TAU+Internet.
2. *Secondary outcomes:* Patients assigned to TAU+C-CHESS will have improved composite scores; improved individual condition outcomes (mm Hg for hypertension, mg/dL for hyperlipidemia (LDL), HbA1c for diabetes, and pain for arthritis); and fewer symptoms from a list than patients assigned to TAU+Internet.
3. *Mediators:* Patients assigned to TAU+C-CHESS will have, compared with patients assigned to TAU+Internet, greater adherence to medications and appointments as well as improved competence,

relatedness, and autonomy.

4. *Moderators:* Improvements in primary outcomes for TAU+C-CHESS vs. TAU+Internet will be greater for women than men, those ≥ 75 vs. 65 to 74, and those with 3-5 chronic conditions vs. 6+.

Aim 3 Analyze data from the RCT and publish results.

Exploratory questions:

- Does C-CHESS reach a large proportion of targeted patients, get a large proportion of targeted clinicians to use C-CHESS, get a large proportion of patients to regularly use C-CHESS, and maintain that performance over time)?
- Does the use of specific C-CHESS services affect outcomes?
- Does the use of C-CHESS affect other health service use?

Primary Aim

Patients assigned to TAU+C-CHESS will have better quality of life and fewer primary care visits than those assigned to TAU+Internet.

C-CHESS will contain the Clinician Report to make it easier for PCPs to respond to important patient changes, pilot data suggested that primary care visits could be reduced. Reducing the number of primary care visits will both lessen provider burden and ultimately reduce healthcare costs.

Secondary Aim

Patients assigned to TAU+C-CHESS will have improved composite scores; improved individual condition outcomes (mm Hg for hypertension, mg/dL for hyperlipidemia (LDL), HbA1c for diabetes, and pain for arthritis); and fewer symptoms from a list than patients assigned to TAU+Internet.

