2.0 SELECTION OF SUBJECTS

Patient Recruitment: We will recruit 330 patients age ≥ 65 .

Patients are eligible for the study if they:

- 1) are ≥ 65 years old
- 2) have been treated in the clinic for at least the previous 18 months with no plans to leave during the study period

- 3) have ≥ 3 of the following chronic conditions:
 - Hypertension
 - Hyperlipidemia
 - Diabetes
 - Arthritis
 - BMI ≥ 30
 - Chronic Kidney disease
 - Chronic pain
 - COPD
 - Congestive heart failure
 - Arrhythmia/atrial fibrillation
- 4) report no current psychotic disorder that would prevent participation
- 5) have no acute medical problem requiring immediate hospitalization
- 6) do not have a visual or motor impairment that prevents them from using a computer
- 7) be able to read and sign the consent form in English
- 8) have no known terminal illness;
- 9) be willing to share health-related study data and
 - Systolic and diastolic BP
 - Weight
 - BMI
 - HDL/LDL
 - HbA1C
 - pain score
 - health care utilization: hospitalizations (admission and discharge), number of ER visits, urgent care visits, PC visits, specialty care visits, long-term care visits, and rehab visits
- 10) allow researchers to share information with their primary care physician

We will document and describe eligible people who choose not to participate.

Clinician Recruitment: 15 providers (salaried, credentialed staff) from 5 different clinic sites will be identified and recruited to complete 3 qualitative interviews each over the course of the study. Site staff will be identified by the clinic and contacted by the UW study coordinator. Details of the study and their participation will be explained and if they agree informed consent will be collected. Staff are eligible for the study if they:

- Allow monitoring of their C-CHESS usage
- Are willing to participate in 3 interviews to share information about technology use at their clinic and feedback related to C-CHESS.
- Have a patient participating in the intervention arm of this study

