Participants who do not already own a computer will be receiving a laptop as part of the study. The laptop has an administration interface that allows our technical team to access devices remotely if a participant calls tech support or reports a problem. If a participant loses their laptop or installs something that is causing problems, we have the ability to remotely wipe the device, lock it down, restore the operating system and/or run a security check. We can also do security updates remotely to make sure patches are up to date on each laptop and security software has not been disabled by the user.

Patient Randomization: Once informed consent and baseline measures have been obtained from patients, they will be randomized to either the experimental (TAU + C-CHESS) or control (TAU + Internet) group, stratified on gender, clinic site, and number of chronic conditions (3-5 vs. 6+). Patients who are in the experimental group will be further randomized into two groups, one will be asked to identify a health outcome to track and share with their physician using the Clinician Report and the other group will not.

When baseline assessment and consent are complete, the researcher will enter the participant number and randomization data into a randomization spreadsheet. The interviewing researcher, once informed of group assignment, will provide setup and training.

The research staff will train participants to use C-CHESS and customize it (e.g. by health condition) during a home visit. Participants will be asked to check in regularly, initially at a daily rate with frequency of at least weekly over the course of the study.

Patient Qualitative: Data will be gathered via an interview at 3 times from 6 patients at each of the 5 clinics (N=30). Each interview is expected to take 30-60 minutes and will take place either in-person at a place of the subjects choosing or via phone.

Recruitment: Participants will be identified through a consent form opt-in question and demographics as reported on the baseline survey. We will seek a mix of genders and number of chronic conditions. We will also look at C-CHESS use data to find a mix of users and non-users. We will contact potential participants by messaging them through the C-CHESS application or phoning them.

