6.0 MEASUREMENT OF EFFECT

All scales being used in this study have good psychometric properties with similar populations. Listed below are the factors to be measured and measurement instruments with references to validation studies.

Quantitative analyses. Two types of analyses are planned: 1) a general, whole-sample analysis of outcomes not specific to any condition, and 2) analyses of condition-specific outcomes that permit integration across condition categories.

The first, general outcome category includes quality of life and primary care use which will be assessed with the same measures and same metrics regardless of conditions.

The second type of analysis is for condition-specific outcomes: mm Hg for hypertension, mg/dL for hyperlipidemia, HbA1c for diabetes, and pain for arthritis. These outcomes will be analyzed in 2 ways. In one approach, scores on each measure will be transformed to Z scores and combined to create the composite score across all 5 outcomes, which will constitute an improper linear model with unit weighting; this is a secondary outcome. Thus, patients will be compared based on the pooled composite. Because we believe that change in the composite will reflect specific conditions and combinations, these factors will be entered as covariates in separate analyses to determine whether particular conditions or combinations of conditions are significantly related to the magnitude of treatment effects on the composite. Because patients often have more than 3 chronic conditions, we will code for the presence or absence of other common chronic conditions (e.g., cancer, pain, depression, anxiety, falls, heart disease, diabetes, and osteoporosis). The particular combinations involved will be entered as dummy variables. The second approach to the analyses of condition-specific outcomes will involve examining condition-specific outcomes individually, with only those individuals in the C-CHESS and comparison groups who have the pertinent diagnosis contributing data to the analysis (e.g., only those with diabetes will contribute data to the analyses involving HbA1c). The analytic approach to symptoms would be similar to the approach to the condition-specific tests. We will set a threshold for inclusion in the composite, and use as individual dependent variables the symptoms that occur in $\geq 10\%$ of the sample.

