Mediation. We will test 4 potential mediators of the intervention's effect on the primary and secondary outcomes. We will also test whether the condition-specific and composite secondary outcomes mediate the intervention's effect on the primary outcomes. Mediation will be tested by individually testing the 2 paths in the indirect effect and will conclude statistical significance only when the null hypothesis of no effect is rejected for both paths in the mediational pathway. To limit the number of analyses, we will use Bolt's approach⁹⁴ of first using a screening approach that examines only mediational models with outcomes and potential mediators significantly affected by the intervention. We will then use separate univariate models to determine which mediate the intervention effect on given outcomes. If 2 or 3 mediators are found, we will simultaneously enter all the significant mediators into the same model. If 4 mediators are found, we will enter the 'strongest' mediator first and then test whether adding remaining mediators shows significant mediational effects.

Moderation. A moderation model holds that the strength of the relation between intervention and outcomes is a function of the level of other variables and tries to explain under what conditions the treatment model functions. We will test whether gender, age (65-74 vs ≥ 75), and number of chronic conditions (3, 4, or 5) moderate the effect of the intervention on outcomes. Also, when standardized composites are used as the dependent variable, type of chronic condition will be used as a moderator to determine if the composite varies meaningfully by condition. Participants will list changes in chronic conditions at 6 and 12 months.

Moderated mediation. Although both constructs of mediation and moderation are of interest in our research, the process is more complex than just these factors. For example, a variable (e.g., relatedness) may act as a stronger mediator for 1 subgroup (e.g., women) than another (e.g., men).

Qualitative analyses. Through 3 interviews we will gather qualitative data from clinic staff to provide additional insights into their use of the CR.

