7.0 STUDY PARAMETERS

Patients will be randomized on a 1:1 ratio to TAU + internet or TAU+C-CHESS. Subjects will be stratified by gender, number of conditions and study site. It is anticipated that up to 330 patient subjects will be recruited at the participating clinics. Staff subjects will have access to C-CHESS for the duration of the study. Patient will have access to C-CHESS for 12 months.

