8.0 STATISTICAL CONSIDERATIONS

Power analyses for primary and secondary outcomes. Our power analysis was based on Elder Tree pilot data and other studies that examined the impact of behavioral interventions on single chronic conditions.⁹⁵ A meta-analysis⁹⁶ of self-management interventions found significant effects on HbA1c for diabetics ($d = .36$), and on systolic blood pressure among hypertensives ($d = -.39$). Other studies found a moderate effect size ($d = .61$) on pain behavior⁹⁷ and a small effect on number of primary care visits ($d = .28$) when patients attended self-management and peer-support meetings.^{98,99}

Because effect sizes vary for interventions of chronic conditions, we want our expected effect sizes to be conservative and yet clinically meaningful. We therefore chose an effect size of $d = .40$ for our primary

outcomes (quality of life and primary care use) as well as individual condition measures (secondary outcomes) and the composite score based on them. Adequate power ($1-\beta = .80$, two-tailed $\alpha = .05$) would require a final sample of $N=200$ patients (100 per arm).¹⁰⁰ Since we will examine 4 clusters, with 3 conditions per cluster, we will need 132 per arm. Assuming 20% attrition, we will recruit $N=330$ patients (33 per arm per clinic). This should also be sufficient for detecting similar effect sizes (at a power of $1-\beta = .80$) for condition-specific changes in diabetes,¹⁰¹ hypertension,¹⁰² and arthritis.¹⁰³ The literature is less clear in hyperlipidemia but 50% of patients are non-adherent to statins,¹⁰⁴ and statins have a high effect size,¹⁰⁵ so our goal may be achievable.

Power for mediation and moderation analyses. Power for detecting parameter changes in the structural model was estimated using a procedure of Satorra and Saris¹⁰⁶ that approximates the non-central chi-square distribution. A total N of 220 patients will provide adequate power ($> .80$) to detect a group difference in a parameter by moderate .4 standard deviations. With an N of 264 in our primary analysis, we are confident our secondary analysis will have adequate power.

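### The moderation analysis codes number of conditions as 3, 4 or 5, while Hypothesis 4 and the randomisation strata contrast 3-5 with six or more

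*Combined protocol and SAP*

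**What the plan says.** All references are to the combined protocol and SAP.

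- Section 1.0, Aim 2, Hypothesis 4 predicts that gains in the primary outcomes will be larger for three subgroups. The third is "those with 3-5 chronic conditions vs. 6" or more (the quote stops before the plus sign).
- Section 3.0, Patient Randomization: allocation is "stratified on gender, clinic site, and number of chronic conditions (3-5 vs. 6" or more). Section 7.0 repeats the factor without cut-points: "Subjects will be stratified by gender, number of conditions and study site".
- Section 2.0: patients must "have ≥ 3 of the following chronic conditions", followed by a list of ten.
- Section 6.0, Moderation: the plan will test whether gender, age (65-74 against 75 and over) and "number of chronic conditions (3, 4, or 5) moderate the effect of the intervention on outcomes". It does not say which conditions are counted. It adds that participants report changes in their conditions at 6 and 12 months, and does not say whether the moderator is the baseline count.
- The opening summary describes a narrower population, with "3 or all of the following 5 common, high-risk chronic conditions: hypertension, hyperlipidemia, diabetes, osteoarthritis and BMI of 30" or more.
- Section 8.0 says that 220 patients give more than 80% power to "detect a group difference in a parameter by moderate .4 standard deviations", and gives 264 as the number in the primary analysis.

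**The concern.** Gender and age are coded the same way in Hypothesis 4 and in the Moderation paragraph. Condition count is not. The Moderation paragraph is the only place that specifies how the moderation test is run, and its three levels contain no category for six or more. Section 7.0 gives no cut that would settle the matter. The dummy variables elsewhere in section 6.0 concern particular conditions and combinations in the composite analysis, not the count contrast.

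At stake is one directional hypothesis about the primary outcomes, on a factor that the trial went to the trouble of stratifying. An analyst who follows section 6.0 does not test it. One who follows section 1.0 departs from the analysis section.

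**Working it through.** **Setting the sections side by side**

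1. Section 2.0 requires at least three of ten conditions, so a patient can have six or more. The existence of a 6+ stratum in section 3.0 implies the same: a list of five could not produce it.
2. Suppose the moderator counts conditions as eligibility does. Levels 3, 4 and 5 are then all at or below 5, so all three lie inside the 3-5 stratum. A count of six or more has no level. Comparing 3 with 4 with 5 is a comparison within one side of the hypothesised contrast.
3. Suppose the top level was meant as five or more. It then pools patients with exactly five (lower stratum) with patients with six or more (upper stratum). The 3-5 versus 6+ contrast still cannot be recovered.
4. Suppose the moderator counts only the five conditions of the opening summary. A patient with hypertension, hyperlipidemia and diabetes alone has three listed conditions. One who also has kidney disease, COPD and heart failure has six. Both would be coded 3, so this coding does not separate the strata either.

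**Reproducing the plan's figures (section 8.0)**

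- d = 0.40, 80% power, two-sided 0.05: n per arm = 2(1.96 + 0.84)²/0.40² = 98, or 99 per arm with unrounded normal quantiles rounded up. The plan states 100.
- 2 × 132 = 264, and 264/0.80 = 330, as stated.
- 220 patients, 0.4 SD: a simple comparison of two groups of 110 has SE = √(2/110) = 0.135 and 0.4/0.135 = 2.97, giving 84% power. This is consistent with the stated figure of more than 80%. The inputs to the structural-model procedure that the plan cites are not given, so that calculation cannot be repeated.

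**What the corrected test could detect**

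Assumptions: unit SD, 1:1 arms within strata, one time point, no covariate, N = 264, and a share p of patients with six or more conditions (not given in the documents).

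- Variance of the difference between the two treatment effects = 4/(Np) + 4/(N(1−p)) = 4/(Np(1−p)). It is smallest at p = 0.5.
- At p = 0.5: 4/(264 × 0.25) = 0.0606, SE = 0.246, and 0.4/0.246 = 1.62. Power = Φ(1.62 − 1.96) = 37%. The interaction detectable with 80% power is (1.96 + 0.84) × 0.246 = 0.69 SD.
- At p = 0.3, 0.2 and 0.1, power is 32%, 26% and 16%.
- With the baseline outcome as covariate, SE is multiplied by √(1−r²). The correlation r is not in the documents. At p = 0.5, assumed values give:

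| r | SE | Power |
|---|---|---|
| 0.5 | 0.246 × 0.866 = 0.213 | 47% |
| 0.6 | 0.246 × 0.800 = 0.197 | 53% |
| 0.7 | 0.246 × 0.714 = 0.176 | 62% |

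**The case against.** **The test is in conflict, not absent.** Section 1.0 commits the trial to testing four hypotheses and states the 3-5 versus 6+ contrast. A reader might infer that the trial has no plan to test it, or that the cut is open to choice after the data are seen. The documents do not support that, because the hypothesis is stated and the split is fixed at randomisation. This stands, and it is why the conclusion is conditional on following section 6.0.

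**The condition list is undefined for the strata too.** Neither section 1.0 nor section 3.0 says which conditions make up the 3-5 and 6+ counts. Section 3.0 extracts the number of conditions as an item separate from the ten-condition list, and also obtains diagnoses of anxiety, depression, osteoporosis and cancer. Section 6.0 codes further conditions. A reader might therefore go on to count how many possible totals have no level, but that assumes the strata count exactly the ten in section 2.0. The objection stands against any such tally. It does not remove the mismatch: on a longer list, six or more is still possible and 3, 4 and 5 still lie below it.

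**The five-condition population is another inconsistency.** Patients with fewer than three of the five conditions in the opening summary arise because that summary and section 2.0 describe different populations. This is fair, and the point does not rest on them.

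**37% is not a ceiling for the planned analysis.** Section 6.0 puts the baseline outcome in each model and uses repeated measures. This stands, so 37% is only the unadjusted best case. A reader might also infer that the moderation power statement in section 8.0 is wrong. The documents do not show that: it concerns a structural-model parameter, and whether that parameter is this interaction is not stated.

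**The effect is small.** One moderator of three, a wording remedy and a weakly powered test argue for low priority. That limits the weight of the point, not its truth.

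**Conclusion.** The point holds. The coding in the Moderation paragraph does not contain the condition-count contrast that Hypothesis 4 states and the randomisation uses, and no section reconciles them. Followed as written, it leaves that part of Hypothesis 4 untested and gives no level to patients with six or more conditions. This rests on conditions being counted as for eligibility, or on any longer list.

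The reach is limited to one of three moderators. The 12-month primary comparison and the sample size of 330 are unaffected. How many patients would lack a level cannot be stated, because the share with six or more is not given. Correcting the coding restores the stated test but probably does not make it well powered: about 37% at best unadjusted, and roughly 47% to 62% at an even split under assumed baseline correlations of 0.5 to 0.7.

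A separate drafting slip lies nearby and does not carry this point. Section 6.0 names four condition outcomes ("mm Hg for hypertension, mg/dL for hyperlipidemia, HbA1c for diabetes, and pain for arthritis") but describes the composite as covering five outcomes, and later five major conditions. A reader might infer that the composite is unusable. The documents do not support that: it is a secondary outcome, and the Secondary Aim in section 1.0 also reports each condition separately.

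**What to change.** In section 6.0, Moderation, replace the parenthesis 3, 4, or 5 with: *3-5 vs. 6+, the baseline value used for stratification at randomisation*. State there which condition list that count uses, and give the same definition where sections 1.0, 3.0 and 7.0 refer to the factor. If an analysis by 3, 4 and 5 is still wanted, label it exploratory and say which conditions it counts. Naming the baseline value also settles whether changes reported at 6 and 12 months alter the moderator.

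The cost is wording only. The stratum has to be known to randomise each patient, so no new data are needed. The change should be made before analysis.

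Drafting note: in section 6.0, make the number and the list of composite outcomes agree, either by naming the fifth or by changing five to four. That choice is the sponsor's.

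### Hypothesis 4 (moderators) has no fixed test family: section 6.0 widens the outcomes and recodes the number of conditions, and no multiplicity rule or exploratory label is given

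*Combined protocol and SAP*

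**What the plan says.** Section 1.0, Aim 2, states the purpose as "Conduct a randomized clinical trial to test 4 hypotheses". The fourth concerns moderators: "Improvements in primary outcomes for TAU+C-CHESS vs. TAU+Internet will be greater for women than men", with parallel claims for patients aged 75 or over against 65 to 74, and for 3-5 chronic conditions against 6 or more. All three claims are directional and confined to the primary outcomes, quality of life and primary care visits. A separate list of exploratory questions follows in the same section, and moderators are not on it.

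Section 6.0, Moderation, describes the analysis differently. It will test whether gender, age group "and number of chronic conditions (3, 4, or 5) moderate the effect of the intervention on outcomes". The words "moderate the effect of the intervention on outcomes" carry no restriction to the primary outcomes. It adds that for standardized composites "type of chronic condition will be used as a moderator to determine if the composite varies meaningfully by condition".

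Section 3.0, Patient Randomization, stratifies on 3-5 versus 6+ conditions, in line with section 1.0 and not with section 6.0.

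Section 6.0, Mediation, has a screening step meant to limit the number of analyses, but it applies to mediation only. Section 8.0 gives one alpha, two-tailed .05, in the paragraph on power for primary and secondary outcomes. Its paragraph on mediation and moderation power gives no alpha and no number of tests, and refers to this work as secondary analysis.

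**The concern.** A listed hypothesis needs a defined test. Here the two sections disagree on which outcomes are tested and on how one of the three moderators is coded, so neither the family of tests nor its error rate can be read from the plan.

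Because moderation is one of the four hypotheses and is not labelled exploratory, a single nominally significant interaction in the predicted direction on a primary outcome could be reported as confirming it, and so as evidence that C-CHESS works better in women, in older patients or in those with fewer conditions. The open wording of section 6.0 also leaves room to report a moderator from a secondary outcome after it has shown nothing on either primary outcome. The plan does not say that this will be done, but nothing in it rules it out.

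**Working it through.** **Coding of number of conditions.** Section 1.0 and the randomization strata contrast 3-5 with 6 or more. Section 6.0 uses the levels 3, 4 and 5. If both count from the same list, all three levels lie inside the 3-5 group and the 6-or-more group never enters the comparison. If section 6.0 counts only the five target conditions named in the introduction, it is a different variable from the one in the hypothesis. On either reading it is not the contrast in hypothesis 4. It is also a three-level factor, so it has no single interaction coefficient with a predicted sign. The calculation below takes the two-level coding of section 1.0.

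**The plan's own alpha.** There is no stated familywise figure to reproduce. The stated sample size does confirm which alpha was used: for d = .40, two-sided .05 and power .80, n per arm = 2(1.960 + 0.842)²/0.40² ≈ 98.1, so 99 with the normal approximation. The t-test gives 99.1, so 100, as stated. Likewise 264/(1 − 0.20) = 330. The 100 per arm therefore rests on an unadjusted two-sided .05.

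**Counting tests.**
- Section 1.0: 3 moderators × 2 primary outcomes = 6.
- Section 6.0, read as all primary and secondary outcomes: 2 primary + 6 secondary (composite, blood pressure, LDL, HbA1c, pain, symptoms) = 8, and 3 × 8 = 24. This count is ours; the documents give none. It omits the condition-type moderator of the composite, the three follow-up times, and the part of section 6.0 that will "use as individual dependent variables the symptoms that occur in" at least 10% of the sample.

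**Error rate, independent tests.** With every interaction null and each test at two-sided .05:
- 6 tests: 1 − 0.95⁶ = 26.5%.
- 24 tests: 1 − 0.95²⁴ = 70.8%.
- 6 tests, counting only the predicted direction: 1 − 0.975⁶ = 14.1%.

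**Error rate, correlated tests.** The documents give no correlations, so these are assumptions. Null z statistics were simulated for three independent moderators with equal correlation between outcomes, plus one version in which all tests correlate at .5. An event is any |z| > 1.96, or any z > 1.96 for the predicted direction.

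| Assumed correlation | 6 tests, two-sided | 6 tests, predicted direction | 24 tests, two-sided |
|---|---|---|---|
| 0 | 27% | 14% | 71% |
| .5 between outcomes | 25% | 13% | 58% |
| .8 between outcomes | 22% | 11% | 40% |
| .5 between all tests | 21% | 10% | 46% |

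Equal correlation is a simplification: the composite is built from the condition-specific measures, and each of those is analysed only in patients with the diagnosis.

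**The case against.** The three moderators are specified in advance with directions, and gender and number of conditions are stratification factors, so this is not an open-ended subgroup search. Section 8.0 places the moderation work below the primary analysis by calling it secondary, and section 6.0 fixes the primary analysis at 12 months. Many readers would treat subgroup tests as exploratory anyway. All of this stands, and it limits the seriousness of the point. But calling the work secondary is neither an error-control rule nor an exploratory label, and section 1.0 lists moderation among the hypotheses and leaves it off its exploratory list.

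A reader might infer more than the documents support:
- That the plan says the moderators are tested at full alpha. It does not; that is the natural reading when no adjustment appears.
- That one figure, such as 25% or 58%, is the error rate. Those values hold only at an assumed between-outcome correlation of .5.
- That 24 is the plan's own family, or that moderated mediation adds a known number of tests. The moderated-mediation paragraph only illustrates the idea and specifies no test.
- That the two-sided or 24-test rates give the chance of falsely confirming hypothesis 4. A result in the wrong direction, or on a secondary outcome, cannot confirm a directional claim about primary outcomes. The figure for that harm is the 10-14%.

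**Conclusion.** The concern holds in a limited form. Hypothesis 4 and its analysis do not match on outcomes or on the coding of number of conditions, and the section 6.0 coding cannot test the stated claim. No adjustment, gate or exploratory label applies. With no true moderation and each test at two-sided .05, the chance of at least one false interaction is about 21-27% for the six primary-outcome tests and about 40-71% for 24 tests. The chance of falsely supporting hypothesis 4 in its stated direction is about 10-14%. These figures rest on an inferred alpha, assumed correlations, the two-level condition coding and, for the last range but one, our count of 24. Every scenario is well above 5%, so the conclusion does not depend on the correlation chosen. The main comparison of the arms on the primary outcomes is not affected. The plan should be changed on this point, but it does not threaten the trial's main result.

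**What to change.** 1. Reconcile the condition-count moderator in section 6.0 with the 3-5 versus 6+ coding used in section 1.0 and in the randomization strata. This comes first, because the six tests are not defined until it is done.
2. In section 6.0, restrict the hypothesis-4 tests to the two primary outcomes, as section 1.0 has it, at the 12-month time point that section 6.0 names for the primary analysis.
3. Label hypothesis 4 and every other moderator test exploratory. Report arm-by-moderator estimates with 95% confidence intervals, and draw no conclusion of differential benefit from an unadjusted p-value. If hypothesis 4 is to stay confirmatory, apply Holm over the six tests instead, so that the smallest p-value is compared with .05/6 = .0083; the other moderator tests remain exploratory.

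The change is to wording only; sample size, data collection and schedule stay as they are. The downside is that a lone nominal interaction can be described only as hypothesis-generating or, under Holm, that each interaction test has less power. The edit should be made before outcome data by arm are seen.
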